
2.2 BACKGROUND

People in their working years are the population most affected by the opioid crisis. The U.S. is in the middle of an opioid crisis, with annual drug overdose deaths increasing dramatically in the past decade, now exceeding the number of annual motor vehicle deaths and surpassing the number of deaths from HIV in any one year at the height of the HIV crisis. In 2017, 95% of the 70,067 U.S. drug overdose deaths

occurred among persons aged 18-64 years.¹ In the 2017 National Survey of Drug Use and Health,² 34% of respondents aged 18-64 years reported using prescription opioids for pain relief in the past year; of those using prescription opioids, 17% report misuse, meaning taking the opioids not as prescribed. Of those reporting opioid misuse or opioid use disorder (OUD), most were currently employed full-time or part-time (66% and 52% respectively). Since the majority of reported opioid use and misuse occurs among the employed working age population, workplace policies, programs, and health benefits should be considered important venues for intervention.

The relation between employment status and opioid use can be leveraged to prevent opioid misuse and promote recovery for opioid use disorder. Most working age people obtain health insurance through their employers, meaning that opioid prescribing practices and treatment for opioid misuse are influenced by employment-based insurance policies for a large proportion of the population at risk. Health-related disability from opioid use has effects on employment, with potential loss of earnings and access to health insurance for individuals and their dependents, and affects the larger economy. We propose to leverage workplace policies as a tool to prevent opioid misuse and aid in recovery for opioid use disorder.

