of national data have shown that rates of opioid overdose deaths are significantly higher among workers employed in industries and occupations with higher rates of work-related injuries and illnesses.³² Second, construction work is often intermittent, and workers are usually paid only for time worked. Analysis of data across all occupations showed that opioid death rates are significantly higher among workers in occupations with lower availability of paid sick leave and lower job security, suggesting that the need to return to work soon after an injury or to work while in pain may contribute to high rates of opioid-related overdose deaths among workers in construction and other industries.³² Third, in addition to having a higher chance of receiving an opioid prescription, construction workers have higher rates of alcohol and tobacco use than the general population,³⁵ putting them at higher risk of developing OUD after initiation of opioids. National organizations of construction unions and employers are becoming aware of this issue and have a strong incentive to address this crisis.^{36, 37} Importantly, the structure of health benefits and employment of union construction workers makes this group well suited to test policy and guideline changes. In collaboration with construction industry leaders and union health plans, in **Aim 2** we will further characterize the opioid problem in construction and create guidelines on opioid use by adapting best-practice healthcare and employment policies to the unique needs of the construction industry.

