5 STUDY POPULATION

The study population are members of the participating union health funds from the construction trades. All of the member workers of the enrolled health funds will be considered eligible participants for the study. For administrative claims data, this will include all members who were benefits eligible from May 2019 through the end of the study period (May 2023). For worker surveys, all active members of the union will be eligible and invited to participate. There will be no exclusions from eligibility.

The members of the union health funds will be at least 18 years of age, with no maximum age limit. The study population characteristics will reflect the demographics of the workforce, with approximately 8% female and 10% non-Caucasian.

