9.4.3 ANALYSIS OF THE SECONDARY ENDPOINT(S)

For each secondary endpoint:

Worker Survey

- a) Proportion of workers with lost time. Responded yes to one of the questions below:
 - a. Please refer to the last 12 months for the following questions: Did you miss any days of work because of your pain or discomfort? [missday_pn]x
 - b. In the past 12 months, have you gone to work intoxicated, high, or recovering from the night before? [missday_intox] [*possible reduced productivity]x
- b) Proportion of workers who are willing to seek help. Responded yes to one of the questions below:

Through their workplace:

- a. If I was struggling with a substance use problem... I would be willing to seek help from my supervisor or someone in human resources [help_sup_hr]x
- b. If I was struggling with a substance use problem... I would be willing to seek help from a professional (MAP or behavioral health) [help_prof]x

- c. If I was struggling with a substance use problem... I would be willing to ask a trusted coworker for help [help_coworker]x
- d. Have you attended Alcoholics or narcotics anonymous (AA/NA) group [aa_na_use]x
- e. Have you met with the specialist? [peer_supp_use]x

Seek professional help (employee assistance program or behavioral health)

- f. If benefit is available.... Union sponsored Member assistance program (MAP) [eap]x; Have you used these benefits? Member assistance program (MAP) [eap_use]x
- g. If benefit is available.... Behavioral health (counseling) [behav_health]x; Have you used these benefits? Behavioral health (counseling) [behav_health_use]x

c) Compute the change at 6 months post-intervention (change of lost time and change in willingness to seek help) of group-level data collected from groups of health fund members.

All endpoints are independent outcomes.

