3. Chronic MSD or recurring acute injuries
4. Other diagnoses

- v. Opioid utilization. Number of workers with:
 1. At least one opioid fill
 2. Ever days supply > 7
 3. Ever MME/day > 50
 4. Ever MME/day > 90
 5. Overlapping Rx
 6. Chronic use (>60 day supply in 90-day period)
 7. Multiple Rx on the same day, same provider
 8. Multiple Rx on the same day, different providers
 9. Misuse
- vi. OUD
 1. N by source (diagnosis, MAT fill, both)

- h. Medical claim/opioid linked data
 - i. Distribution of opioid fills by diagnosis, as captured on linked claim

- b) Worker Surveys
 - a. Worker surveys will be distributed to all members of each health fund at start of project, to collect a sample of 300 surveys. We will collect another sample of 300 surveys after 6 months.
 - b. We will examine the serial cross sectional data (baseline & 6mos) by comparing sample characteristics.
 - Age, x
 - gender, x
 - race, x
 - hisp, x
 - unionbenefits, x
 - employstatus, x
 - time_construction, x
 - months_construction, x
 - constype;x
 - c. We will examine the items related to each of the three outcomes of interest
 - i. Opioid misuse- A “yes” response to either of the following two items:
 1. Did you use the pain medication more than prescribed, or for a longer period than prescribed? [pnmed_longer]x
 2. Have you used prescription pain medications that were prescribed to someone else? [pnmed_othersrx]x
 - ii. Proportion of workers with lost time- A “yes” response to either of the following two items:

1. Please refer to the last 12 months for the following questions: Did you miss any days of work because of your pain or discomfort? [missday_pn]x
2. In the past 12 months, have you gone to work intoxicated, high, or recovering from the night before? [missday_intox] [*possible reduced productivity]x
- iii. Proportion of workers who are willing to seek help
 - 1) their workplace
 1. If I was struggling with a substance use problem... I would be willing to seek help from my supervisor or someone in human resources [help_sup_hr]x
 2. If I was struggling with a substance use problem... I would be willing to seek help from a professional (MAP or behavioral health) [help_prof]x
 3. If I was struggling with a substance use problem... I would be willing to ask a trusted coworker for help [help_coworker]x
 4. Have you attended Alcoholics or narcotics anonymous (AA/NA) group [aa_na_use]x
 5. Have you met with the specialist? [peer_supp_use]x

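### Lost time can be scored only for time in work, but the denominator is all responding members, so a shift in employment mix between waves can move this secondary endpoint

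*Combined protocol and SAP*

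**What the plan says.** Section 9.4.3 a) defines the proportion of workers with lost time as a yes to either of two items:

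- "Did you miss any days of work because of your pain or discomfort" (asked about the past 12 months)
- "In the past 12 months, have you gone to work intoxicated, high, or recovering from the night before"

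The data-management appendix in 10.2 repeats the rule. The worker survey in 10.2 shows only Yes and No for both items, with no not-applicable option.

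Section 9.4.1 computes each survey outcome as the proportion of members responding positively. Section 5 states that "all active members of the union will be eligible and invited to participate", with no exclusions. Nothing limits the denominator to respondents who had work.

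Section 8.1 lists employment status among the survey topics. The data-management appendix names the variable "employstatus" only among the sample characteristics to be compared between baseline and 6 months. Under 9.4.8 survey responses are not linked to the administrative data, so work-hours records cannot supply the missing exposure.

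**The concern.** The numerator is conditional on having work and the denominator is not. A respondent without work in the past 12 months had no days to miss and no shift to attend impaired, yet appears to count as a member without lost time. Someone who worked for part of the year had less time in which to score.

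This matters here because section 2.2 says that "construction work is often intermittent, and workers are usually paid only for time worked", and the guideline text in 10.2 says workers with opioid use disorder are more likely to lose employment. The two waves are separate voluntary samples recruited through channels chosen fund by fund (5.5, 8.1). The share with little or no recent work can therefore differ between waves even if nobody loses a job.

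Section 9.4.1 says a change in proportion may be due to the intervention. A shift in employment mix could then be read as less lost time. For claims outcomes, 9.4.1 adjusts for the length of each period. The survey endpoint has no counterpart.

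**Working it through.** **Figures the plan gives.** Section 9.2 sets 300 surveys per fund per wave. With three funds that is 300 × 3 = 900 per wave, and 900 × 2 = 1800 in total, which matches the stated minimum. A third wave gives 2700, also as stated. (Section 5.5 gives 900 for both time points together, which does not agree with 1800; the 9.2 figure is used here.) The plan states no lost-time rate, employment rate, alpha or power, so there is nothing further to reproduce.

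**Assumed inputs**, none of them in the documents:

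- q = 12-month yes risk for a member with work all year. Central value 30%, range 10% to 50%.
- u = added share of respondents out of work at the later wave. Central value 10 points, range 2 to 20.
- r = yes risk among those added members.

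**Formula.** Observed proportion = (1 − u) × q + u × r. The false fall is q minus this, which equals u × (q − r). For m months worked in the window at a constant hazard, r = 1 − (1 − q)^(m/12).

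**Three cases at q = 0.30, u = 0.10:**

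1. *No work in the whole 12 months.* r = 0. Observed = 0.90 × 0.30 = 0.270. Fall = 3.0 points.
2. *Job lost exactly at baseline, so 6 of the 12 recall months were worked.* r = 1 − 0.70^0.5 = 0.163. Observed = 0.270 + 0.10 × 0.163 = 0.286. Fall = 1.4 points.
3. *Job loss spread evenly over the 6 months, so 6 to 12 months were worked.* The average of r over that range is 1 − (0.8367 − 0.70)/(0.5 × 0.3567) = 0.234. Observed = 0.270 + 0.10 × 0.234 = 0.293. Fall = 0.7 points.

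**Range of the false fall over q = 10% to 50% and u = 2 to 20 points:**

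| Case | Smallest (points) | Largest (points) |
|---|---|---|
| 1. No work all year | 0.2 | 10.0 |
| 2. Job lost at baseline | 0.1 | 4.1 |
| 3. Job loss spread over 6 months | 0.05 | 2.0 |

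**Scale.** The standard error of the difference between two independent waves of 900, at 30% and 27%, is √(0.30 × 0.70/900 + 0.27 × 0.73/900) = 0.0213, or about 2.1 points. It is about 1.4 points at q = 10% and 2.4 at q = 50%.

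**Effect of a work-based denominator.** If only respondents with any work in the past 12 months are counted, case 1 returns to 30% at every u. In cases 2 and 3 everyone still qualifies, so the 0.7 to 1.4 points remain.

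**The case against.** The strongest reply is the recall period. Both items look back 12 months and the waves are 6 months apart. A reader might infer that every member out of work at the survey is a forced no, or that a worker who misses days and then loses the job is recorded as improved. The documents do not support either inference. Days missed in the six months before baseline, or between waves, are still inside the follow-up window and still score yes. A member off work because of pain may also answer yes to the first item. Individuals are not followed, so nobody is recorded as improving.

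A reader might also take the employment figures in section 2.2 (66% and 52%, hence 34% and 48% not employed) as the out-of-work share. They describe current employment among national survey respondents with misuse or opioid use disorder. They do not describe active union members or a full year without work, and should not be used for this endpoint. Members who leave the union leave the denominator altogether, which is selection rather than a forced no.

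The scoring is also not fully visible. No rule is stated for a single skipped item; section 7.2 covers only surveys more than half incomplete. The opening part of the worker survey was not available to this review, so skip logic and the wording of the employment item could not be checked. That a member without work counts as a non-event is the natural reading of 9.4.1, not an explicit rule.

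Finally, comparing employment status between waves would reveal a shift, and 9.1 plans no formal hypothesis testing.

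These points limit the size and the consequence. They leave the mismatch between numerator and denominator in place. A comparison of sample characteristics can show that the mix changed, but not how much of the change in lost time follows from it. The recall argument addresses new job loss; it does not cover two voluntary samples that differ in the share with no work all year, where case 1 applies to whatever that difference is.

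**Conclusion.** The point holds in a limited form. The lost-time proportion depends on how many respondents had work, and for how much of the year, as well as on lost time among those working. More time out of work pushes it down.

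At the assumed 30% yes rate and 10-point rise, the artefact is 3.0 points only if the added members had no work for the full 12 months. For job loss between waves it is about 0.7 to 1.4 points, which is below the standard error of about 2.1 points. Both inputs are assumptions and the constant hazard is a simplification, so these figures show scale and do not predict a bias.

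The endpoint is secondary and descriptive, in a feasibility trial not powered for outcome change. The issue does not threaten the trial's purpose. It is worth correcting because 9.4.1 allows a change to be linked to the intervention, the results are meant to inform the power of a later trial, and the needed variable is already collected.

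**What to change.** In 9.4.3 a):

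- Keep the all-member proportion as defined.
- Report beside it, at each wave, the out-of-work share and the lost-time proportion by employment status.
- If the survey items identify respondents with any work in the past 12 months, also report the proportion with that denominator.
- Do not filter on current employment status alone. That would drop recently laid-off members who did miss days.
- State how a blank on either item is scored.
- Acknowledge that part-year exposure remains. Do not attribute a change in the all-member figure to the intervention unless it also appears within employment strata.

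The cost is a few sentences of plan text, slightly more tabulation and smaller, less precise strata. No new data collection is needed.

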1 PROTOCOL SUMMARY

Title:	Improving Health and Employment Outcomes Through Workplace Opioid Policies
Grant Number:	1R34DA050044-01
Study Description:	We will implement the intervention in three local union health funds, evaluate the implementation using the RE-AIM framework, and collect the data needed to measure effectiveness of the workplace opioid guidelines. We will measure a) the health fund's adoption of policies and programs; b) opioid prescriptions, chronic opioid use, and OUD in health claims and pharmacy data; c) changes in knowledge, attitudes, and beliefs of employers, health fund administrators, and employees; and d) employee participation in employee assistance programs and healthcare recovery services.
Objectives*:	The overall aim is to evaluate the feasibility of implementing workplace opioid guidelines in the construction trades; define and collect measures of implementation and effectiveness. The primary objective is to evaluate a change in opioid misuse and opioid use disorder from medical and pharmacy claims, and worker surveys following a change in policies and programs within health funds. The secondary objective is to evaluate a change in lost time and willingness to seek help among workers who are struggling with opioid misuse or substance use problems on worker surveys.
Endpoints*:	The primary endpoints are a) the change in the proportion of workers with opioid misuse, opioid use disorder and opioid overdose: administrative data and b) in the proportion of workers with opioid misuse: worker surveys from baseline to 6-months. The secondary endpoints are a) the change in the proportion of workers with lost time: worker surveys and b) the proportion of workers who are willing to seek help: worker surveys from baseline to 6-months.
Study Population:	Participants will be members of three participating union health funds. We anticipate these unions will have 33300 members enrolled between 2019-2023, which is the period of data used for the trial. All union members of the participating health funds will be enrolled in the study. We expect the demographics of the participants will reflect the demographics of the membership, which is approximately 8% female, and 90% Caucasian. All participants will be located within the geographical region of the union membership.
Phase* or Stage:	This is a feasibility trial.

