- Neither Agree nor Disagree
- Agree
- Strongly agree

If I was struggling with a substance use problem...

	Yes	No
I would be willing to seek help in human resources		from my supervisor or someone
I would be willing to seek help in behavioral health		from a professional (MAP or
I would be willing to ask a trusted coworker for help		

You have completed the survey. Thank you. Please press submit

C. Administrative Claims_Data Variables

Label	Variable name	database	Description
Patient Identifier	Patient ID	Claims	Unique identifier created by health plan to allow linkage of the datasets (pharmacy and claim data)
Claim date	claimDate	Claims	date of claim
Claim type	claimType	Claims	code for type of claim
Provider identifier	providerSrv ID	Claims	Unique identifier in health plan database for provider
Primary diagnosis (ICD-10)		Claims	primary ICD-10 code
All diagnoses (ICD-10 codes)	allDiagnosis	Claims	ICD-10 codes for the visit
CPT and HPCCS codes	procedureCode	Claims	CPT and HPCCS codes
Claim start date	serviceFrom	Claims	start date of claim episode
Claim end date	serviceThru	Claims	end date of claim episode
Claim episode	Sequence	Claims	number to group rows of data for each single episode
Patient Identifier	Patient ID	Pharmacy	Unique identifier created by health plan to allow linkage of the datasets (pharmacy and claim data)
Pharmacy date of service	Date of Service	Pharmacy	Pharmacy date of service
Pharmacy location identifier	Pharmacy RX No	Pharmacy	Pharmacy location identifier
Drug name	Drug Name	Pharmacy	drug name
Drug type	Drug Type	Pharmacy	drug type
Drug identifier	NDC	Pharmacy	drug identifier
Refill number	Rx Refill Nbr	Pharmacy	number of the refill
Formulary category	Formulary Ind	Pharmacy	single or combination drug
Indication for drugs	Most Common Indication	Pharmacy	category of indication for drugs (i.e. pain/inflammation)
drug for maintenance	Maintenance Drug	Pharmacy	purpose of drug
number of days	Days Supply	Pharmacy	number of days supply
number of tablets	Fill QTY	Pharmacy	number of tablets per drug
Claim correction	Claim count Nbr	Pharmacy	Used to correct misentries in data
Relationship code	Relshp Cde	Pharmacy	relationship of the patient (member, spouse, dependent) to identify possible non-member data in the dataset
Age	Age	Pharmacy	Computed by the health fund, age at time of first claim
Gender	Gender	Pharmacy	sex of patient

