 - 2) professional help (employee assistance program or behavioral health)
 6. If benefit is available.... Union sponsored Member assistance program (MAP) [eap]x; Have you used these benefits? Member assistance program (MAP) [eap_use]x
 7. If benefit is available.... Behavioral health (counseling) [behav_health]x; Have you used these benefits? Behavioral health (counseling) [behav_health_use]x

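### The lost-time endpoint counts workers who went to work impaired, and the willingness endpoint counts past use of services

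*Combined protocol and SAP*

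**What the plan says.** Section 9.4.3 defines two secondary survey endpoints, each met by a yes to one of a list of items.

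- **Lost time** has two items. `missday_pn` asks about days missed because of pain or discomfort. `missday_intox` reads "In the past 12 months, have you gone to work intoxicated, high, or recovering from the night before? [missday_intox] [*possible reduced productivity". The data management appendix, part b) Worker Surveys, repeats the rule as a yes to either item.
- **Willing to seek help** has seven entries under two sub-headings. The workplace sub-heading holds three willingness items, `help_sup_hr`, `help_prof` and `help_coworker` (the last worded in the survey as "I would be willing to ask a trusted coworker for help"). It also holds two past-use items, "Have you attended Alcoholics or narcotics anonymous (AA/NA) group" and "Have you met with the specialist? [peer_supp_use]x". The second sub-heading, "Seek professional help (employee assistance program or behavioral health", pairs a benefit-availability question with a use question: "Have you used these benefits? Member assistance program (MAP) [eap_use]x" for the assistance program and "Have you used these benefits? Behavioral health (counseling" for counseling. The appendix lists the same items but gives no scoring rule for this outcome.

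The Protocol Summary (Section 1) lists attitudes as measure c) and "employee participation in employee assistance programs and healthcare recovery services" as a separate measure d). Section 4.3 gives the guideline's goals as fewer missed work days due to opioid use and more willingness to seek treatment.

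**The concern.** Going to work intoxicated is not time lost from work, and having used counseling is not a statement of willingness. The added items may also move for their own reasons. The guideline's executive summary says that workers without sick leave more often attend in pain and possibly under the influence, and its drug-testing element aims to deter attendance by workers unfit for duty. Impaired attendance can therefore fall while missed days do not. The guideline likewise sets out ways to raise use of assistance programs, so `eap_use` can rise with no change in willingness. Assistance-program and counseling use need not concern substances at all.

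Section 9.2 says the data will inform power calculations for a future R01. A baseline rate or change taken from these composites would describe a different quantity from the one named.

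**Working it through.** **1. Sort the items.** One of the two lost-time items is not about time lost. Four of the seven willingness entries (`aa_na_use`, `peer_supp_use`, `eap_use`, `behav_health_use`) are scored on past use.

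**2. Try both readings of the willingness rule.** The two sub-headings allow one seven-item composite or two sub-outcomes.
- As one composite, a worker who answers no to all three willingness items still counts as willing after a single yes on use.
- As two sub-outcomes, the workplace one still contains two past-use items. The professional-help one contains no willingness item, because `help_prof` sits under the workplace sub-heading.

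Neither reading gives a measure of willingness alone.

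**3. Identity.** Let A be the named outcome and B the added items. No prevalence or independence is assumed.

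P(A or B) = P(A) + P(B and not A)

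So the change in the composite = change in P(A) + change in P(B and not A).

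**4. Survey numbers.** Section 9.2 plans 300 surveys × 3 funds × 2 time points = 1800, which reproduces its stated minimum. (Section 5.5 gives 900 for the same two time points, which this product does not reproduce; I use Section 9.2.) Each wave has 300 × 3 = 900 surveys, so 1 percentage point is 9 respondents, or 3 in one fund of 300.

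**5. Illustrations with assumed counts, not estimates.**
- *Reversal:* `missday_pn` rises by 18 workers (18/900 = +2.0 points), and those who worked impaired without missing days for pain fall by 45 (−45/900 = −5.0). Reported lost time changes by (18 − 45)/900 = −3.0 points although missed days rose.
- *Dilution:* 45 more workers are willing (45/900 = +5.0 points), but 15 of them already counted through service use. The composite shows (45 − 15)/900 = +3.3 points.

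**6. Scale.** The largest 95% margin for a difference between two waves, at p = 0.5 with simple random samples, is 1.96 × √(2 × 0.25/n).
- n = 900: 4.6 points, about 42 respondents.
- n = 300: 8.0 points, 24 respondents.

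**7. A second illustration, assuming independent items.** Composite = 1 − (1 − a)(1 − b), so with b unchanged, a change in a is multiplied by (1 − b).

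| Unchanged added-item rate b | Composite change for a 6.0-point change in a |
|---|---|
| 5% | 5.7 |
| 10% | 5.4 |
| 20% | 4.8 |
| 30% | 4.2 |

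Across b = 5% to 30%, with a starting at 30% for missed days, workers positive only on the impaired item make up 10% (0.70 × 0.05/0.335) to 41% (0.70 × 0.30/0.51) of lost time. With a starting at 60% for willingness, use-only workers make up 3% to 17%. If missed days fall from 30% to 24% while impaired attendance rises from 10% to 17%, the composite goes from 37.0% to 36.9% and hides the fall.

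**The case against.** The strongest defence is that the mix is deliberate. The objectives table in Section 3 introduces the secondary endpoints as behaviors and attitudes, and the Protocol Summary ties them to workers struggling with misuse. On that view the impaired-at-work item is the only substance-linked part of lost time, and AA/NA attendance is real help-seeking. The plan also tags the impaired item openly, and the appendix says it will examine the items behind each outcome. This explains how the items came together, but the named endpoints remain lost time and willingness, and the appendix sentence introduces the definitions without committing to component results.

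Three points stand as limits:
- There is no formal testing, and trial success does not depend on these composites. Item-level rates could be computed later from the retained data.
- The counts above are invented, and both the 3.0-point fall and the 1.7-point dilution lie inside the 4.6-point margin. The guideline cites general assistance-program utilization below 10%, so `eap_use` alone may add few workers, although that figure does not bound this sample.
- Lost time based on `missday_pn` alone has no substance content and, like the present version, does not measure days missed because of opioid use. An accurately labelled composite with its components shown would also cure the labelling fault.

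**Conclusion.** The concern holds. As written, the plan counts attendance as lost time and can count a worker who answers no to every willingness item as willing. This follows from the item lists and rests on no assumed rate. The size is not known: the identity and the 9 respondents per point are exact, while the 3.0-point reversal, the 3.3-point dilution and the 5.7 to 4.2 point range depend on assumed counts or rates. The margins also assume simple random samples, which voluntary recruitment by fund-chosen methods does not provide. Because the endpoints are secondary and descriptive, the consequence is misreading of results and wrong inputs to the future power calculation. The change should be made, but the trial's conduct does not depend on it.

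**What to change.** In Section 9.4.3 and in part b) of the data management appendix:

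- Define lost time as `missday_pn`, labelled as missed work due to pain or discomfort. Report `missday_intox` beside it as worked impaired, so that the substance-related item stays in view.
- Define willingness as yes to any of `help_sup_hr`, `help_prof` or `help_coworker`, and report each item.
- Report `aa_na_use`, `peer_supp_use`, `eap_use` and `behav_health_use` as a separate service-use outcome. State whether workers without the benefit are in the denominator, and what part the `eap` and `behav_health` availability questions play.
- State the scoring rule once, in identical words in both places.
- Keep the present composites as supplementary results, so that nothing pre-specified is lost.

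The cost is SAP wording, recoding of items already in the survey and a few table rows. Section 8.1 describes collection in the past tense, so the change should be dated and disclosed as made after data collection began, if that is the case.
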